Multiple criteria or multicriteria decision analysis (MCDA) – also known as multiple criteria decision making (MCDM) – is the collective name of formal approaches that support decision making by taking into account multiple criteria in an explicit and transparent way. The methodology of MCDA has extensively been used in various disciplines, but given their increased complexity as compared to other methods, they have not been as used in healthcare. Swing weighting is a MCDA method and takes the criteria levels into account when estimating criteria weights. Patients are first exposed to a hypothetical worst-case scenario, where all attributes of preference are set to the worst possible levels. They are then asked to identify the most important criterion to them by selecting the one that, if improved, would improve the overall situation the most. The most important criterion is assigned 100 points, and then decision-makers are asked about the next criterion to be moved from its worst level to its best – that will receive a point value <100. Different options (e.g. treatments) are then scored against each criterion and the weights are used to summarize scores for the purposes of comparing these options. The options (e.g. treatments) are then scored against each criterion and the weights are used to summarize scores for the purposes of comparing these options.

4.1.2.6.

Variables

The web-based survey will include the following sections and variables:

- A DCE exercise to evaluate PP and estimate utilities;
- A short TTO exercise to evaluate health valuation utilities (subset of patients);
- A MCDA exercise to evaluate PP and estimate utilities (subset of patients);
- A ranking exercise in which respondents will be asked to rank order the attributes;
- A set of questions regarding:
 - Respondents' socio-demographics, clinical (.e. diagnosis, cancer stage, number of previous treatments), self-assessed health status, constructs related to choices that

Template No.: PCE_TP_CSC0016 Revision 2 Reference:

PCE_OP_CSC0014

Effective Date: 15Dec2019

may explain heterogeneity (i.e. age, disease severity, family background, patient's understanding of the disease, health awareness and literacy);

- Question to assess respondents' level of understanding of the DCE, MCDA/TTO tasks;
- Question to assess how difficult respondents found to complete the DCE, MCDA/TTO tasks

Sample

Study Eligibility Criteria

4.2.

4.2.1.

Qualitative Evidence Generation

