A pilot phase will be conducted with 20 patients. Based on the feedback from the pilot-testing, modifications to the online survey will be made to finalize the electronic migration. No concurrent manual data review will be performed, and no queries will be followed up with patients for resolution.

High data quality standards will be maintained, and processes and procedures will be utilized to repeatedly ensure that the data are as clean and accurate as possible when presented for analysis. When all data have been validated, signed and locked, the data file will be declared as being a clean file. The final database will then be locked.

Template No.: PCE_TP_CSC0016 Revision 2 Reference:

PCE_OP_CSC0014

Effective Date: 15Dec2019

File Retention and Archiving

To enable evaluations and/or audits, all records, including source documents and adequate documentation of relevant correspondence (e.g., letters, meeting minutes, telephone calls reports) will be kept in IQVIA's secure servers. The records will be retained according to local regulations, or as specified in the study contract, whichever is longer.

All records will be kept and made available for review in the event of audits, or inspections and will be safely archived for at least 5 years after the completion of the study.

Monitoring and Reporting of AE / SAE

4 The sponsor will follow standard procedures for handling adverse events reporting involving these patients – specifically, reporting adverse events to drug safety.

In the event that the patient reports intent or actual harm to themselves or others, IQVIA will ask for the clinician contact during the interview and will report the incident to the patient's clinician or a local suicidal/crisis center to the best their capabilities.

5. Data Analysis

The sample for both phases will be described by means, standard deviations, median, and range, for continuous variables, and by number and proportion of the total study population for categorical ones. 5.1.

Qualitative Evidence Generation Analyses

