Bayesian MNL models will also be used to control for differences in error variance and explore consistency of treatment choices for the DCE methodology. Random utility theory assumes that there may be an additional component of utility that is unobservable. Therefore, the utility function comprises of two elements: a deterministic component based on the participants' preferences for the observed attributes of the alternative, and random error associated with the alternative. ^[46] In the MNL model, it is assumed that choice questions measure utility equally well (or equally poor) across all participants and choice tasks. However, if the variance is not constant across all participants or choice tasks, differences in model estimates between participants or choice tasks may appear different and could lead to biased results. It is therefore important to control for error variances. Regression models will aim to be conducted to examine the relationship between the utilities from the MCDA and TTO methods and patients' understanding and differences when completing the choice tasks, using regression coefficients and 95% confidence intervals. Regression assumptions will be assessed, and appropriate regressions models will be based on the assumptions and data distributions of the utilities.

Exploratory Analyses

An additional objective is to compare and contrast preference weights and patient associations with stated preference using different stated preferences methods. Preference weights estimated from the three methods and association between preferences and patients' characteristics will be compared both descriptively and using anchor-based mapping regressions. Mapping predicts HRQoL states by statistically relating DCE scores to MCDA and TTO scores using a regression mapping method. The aim is for coefficients for each attribute to be calculated by multiplying the DCE coefficients by MCDA and TTO scores in separate regression models. The regression assumptions of the utilities for each method will first be examined and will aim to use appropriate models based on the assumptions and data distributions. Scatterplots of the residuals for the utilities from each method will be further examined. If the utilities violate assumptions and data distributions for regression, transformations may be considered. Otherwise, non-parametric techniques will be used.

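### The discrete choice analysis is to control unequal error variance with a model the protocol says assumes equal error variance; it names no scale term, and the listed survey content has no direct test of choice consistency

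*Protocol*

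**What the plan says.** Section 5.2.2.1 (Secondary Analysis) plans Bayesian multinomial logit (MNL) models in which attribute levels interact with clinical and socio-demographic variables. Cancer type, age, sex, country and education level are given as examples, and cognition, health literacy and numeracy are listed among the factors to be explored. It then adds: "Bayesian MNL models will also be used to control for differences in error variance and explore consistency of treatment choices for the DCE methodology". Of the same model it says that "it is assumed that choice questions measure utility equally well (or equally poor) across all participants and choice tasks", that results can be biased where this fails, and that error variances should therefore be controlled.

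The self-rated understanding item is given an analysis, but not for the DCE. The regressions concern "the relationship between the utilities from the MCDA and TTO methods and patients' understanding and differences when completing the choice tasks".

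Section 4.1.2.6 (Variables) opens with "The web-based survey will include the following sections and variables" and then lists the DCE, the time trade-off (TTO) or multi-criteria (MCDA) task, and background characteristics. It also lists "A ranking exercise in which respondents will be asked to rank order the attributes", "Question to assess respondents' level of understanding of the DCE, MCDA/TTO tasks" and "Question to assess how difficult respondents found to complete the DCE, MCDA/TTO tasks". No repeated, dominated or hold-out choice pair is mentioned there or elsewhere in the protocol.

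Under Data Management, the survey platform allows real-time review for quality and completeness, and quality control is to remove illogical or erroneous entries. The section also states: "No concurrent manual data review will be performed".

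**The concern.** The paragraph sets a task and assigns it to a model that, as described, cannot do it. An MNL with constant error variance estimates preference strength multiplied by scale. A group that answers more erratically has all its coefficients pulled towards zero, and an attribute-by-group interaction reads that as weaker preference.

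The secondary objective depends on these interactions. Education, literacy, numeracy and cognition are plausible correlates of response error, so the bias the protocol warns of would fall where it looks for heterogeneity.

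Nor does any listed item directly show whether a respondent chooses attentively or consistently in the DCE, although the DCE is the leading method and the survey is completed online without a researcher present.

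**Working it through.** **1. The passages side by side (section 5.2.2.1)**
- Task: control differences in error variance and explore consistency of DCE choices.
- Tool: Bayesian MNL.
- The protocol's description of the MNL: error is the same for all participants and tasks.
- Device to relax this (scale term, heteroscedastic logit): none named.

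The protocol gives no figure on this point, so there is none to reproduce.

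**2. Why the plain interaction misleads**

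For group g with preferences β_g, scale λ_g and attribute difference x, P(choose A) = 1 / (1 + exp(−λ_g x′β_g)). Only the product λ_gβ_g is estimated. The plain interaction is λ₂β₂ − λ₁β₁. If β₁ = β₂ = β, it equals (λ₂ − λ₁)β, which is not zero when the scales differ.

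**3. Illustrative size**

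From the protocol: about 900 respondents and two alternatives per set. Assumed: 10 tasks, five three-level attributes, coefficients per level of 0.9, 0.6, −0.7, −0.5 and 0.3, and random responders who choose at 50%. A likelihood-based binary logit stood in for the Bayesian MNL.

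Ratio of pooled estimate to truth:

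| Random responders | Ratio |
|---|---|
| 0% | 1.01 |
| 5% | 0.90 |
| 10% | 0.82 |
| 20% | 0.68 |

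Take identical preferences, with 5% random responders among 300 patients and 20% among 600. A true coefficient of 0.9 then appears as about 0.9 × 0.90 = 0.81 in one group and 0.9 × 0.68 = 0.61 in the other. The implied relative scale is 0.68 / 0.90 = 0.76.
- Plain joint interaction test at 5%: rejects in 98% to 99.5% of runs across repeated simulations.
- Test of different preferences with one free relative scale: rejects in 3% to 4.5%, with estimated scale about 0.75 to 0.76.

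Testing attributes one at a time, at least one of five was significant in 99% of runs. The joint test is the fairer measure, because five independent tests with no true difference would give 1 − 0.95⁵ = 23% anyway.

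**4. Does the scale model hide real differences?**

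Two groups of 450, 10 tasks, coefficients 1.0, 0.8, 0.6, 0.4 and 0.2, 100 runs:
- Same preferences, second group at half scale: plain test rejects 100%, scale-adjusted test 4%, estimated scale 0.50.
- Coefficients reversed in the second group, same scale: scale-adjusted test rejects 100%, estimated scale 1.01.

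**5. Pooled estimates**

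With 30% random responders among 900, these coefficients became 0.54, 0.42, 0.33, 0.22 and 0.10. The odds ratio for the first attribute falls from exp(1.0) = 2.72 to exp(0.54) = 1.72. Its share of the total hardly moves: 1.0/3.0 = 33% against 0.54/1.61 = 34%. In this example relative importance survives, while the odds ratios shrink.

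**6. What a dominated pair could show**

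If attentive patients never fail, the failure rate is half the random share. At a 10% share the standard error is √(0.05 × 0.95/900) = 0.00726, so the share has a 95% half-width of 2 × 1.96 × 0.00726 = 0.028, about 3 points. That needs a wide gap between the profiles:
- One level apart on every attribute: utility difference 0.9 + 0.6 + 0.7 + 0.5 + 0.3 = 3.0. Attentive patients fail 1/(1 + e³) = 4.7%, and a true 10% share reads as 2 × (0.05 + 0.90 × 0.047) = 18.5%.
- Best versus worst: difference 6.0. Attentive patients fail 0.25%, and the reading is 2 × (0.05 + 0.90 × 0.0025) = 10.4%.

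**The case against.** The strongest reply is deferral. Section 5.2 leaves the full analysis to the statistical analysis plan, and section 5.2.2.1 already recognises unequal error variance. How scale enters the model could be specified there. This stands for the detail, but not for the mismatch: the protocol names a method and itself describes it as resting on the assumption that needs relaxing.

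A reader might infer more than the documents support, in four ways.
- **That inconsistency cannot be separated from preference without extra choice tasks, so no analysis plan could repair this.** At group level that is wrong. Step 3 shows that a relative scale parameter, estimated from ordinary DCE choices, removes the false interactions. Check pairs serve another purpose, which is to find individual inattentive or inconsistent respondents.
- **That the survey will contain no check.** Section 4.1.2.6 lists sections and variables, with the DCE as a single line. The choice sets are still to come from the experimental design, the pilot may change them, and the survey is a separate deliverable. Silence at this level does not prove absence.
- **That the orthogonal main-effects design rules out dominated pairs.** The pairing method is not stated. If five three-level ordered attributes were paired at random, the dominated share would be 2 × (2/3)⁵ − 2 × (1/3)⁵, about 25%.
- **That self-rated understanding is the only safeguard.** There are also a difficulty item, an attribute ranking, a second elicitation task, a comprehension pilot and platform quality checks. None directly tests DCE consistency, and a forced choice between two profiles offers no out-of-range answer to catch.

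Added burden is a fair counterweight, since section 7.2.2 lists it as a risk.

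**Conclusion.** The point holds in limited form. The method named for controlling error variance and exploring DCE consistency does not, as the protocol describes it, do that job. The listed survey content mentions nothing that tests consistency directly. If response error differs across the characteristics studied, the interaction analysis run as written can present scale differences as preference differences.

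The size is illustrative only. False rejection of 98% or more rests on an assumed 5% against 20% random share, assumed coefficients and 10 tasks. The simulations also give all attentive respondents the same preferences. A smaller imbalance would do less harm. The consequence falls mainly on the secondary objective and on the size of the reported odds ratios, less on relative importance.

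This should be corrected before fielding, because an analysis plan can add a scale model later but cannot add choice tasks once the survey has closed.

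**What to change.** - **Section 5.2.2.1.** For the interaction and consistency analyses, replace the plain MNL with a model in which scale may differ by the characteristics examined. Test preference differences after allowing for scale. This needs no new data.
- **Section 4.1.2.6, before fielding.** Add to the DCE exercise one clearly dominated (best-versus-worst) pair and one repeat of an earlier pair with sides swapped. Keep both outside the set of pairs used for estimation.
- **Reporting.** Give failure and agreement rates by country, recruitment source, task order and literacy. Keep all respondents in the primary analysis, and add a sensitivity analysis without those who fail.

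The cost is up to two more tasks in a survey of about 20 minutes, plus a short sensitivity analysis. The 20-patient pilot can check the added burden.

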7.3. Protection of Patients

7.3.1.

Confidentiality

The privacy rights of individuals and the confidentiality of medical records will be protected in accordance with all applicable laws, regulations, and guidelines.

Sites and laboratories or entities providing support for this study, which process personal data relating to EU-based patients must comply with the EU General Data Protection Regulation in performing all their processing activities in connection with this study.

After patients have been informed about how their data will be processed and have consented to take part in the study, the sponsor and/or its representatives reviews their medical records and data collected during the study. These records and data may, in addition, be reviewed by others including the following: independent auditors who validate the data on behalf of the sponsor; third parties with whom the sponsor may develop, register, or market; national or local regulatory authorities; and the IRB(s)/EC(s) which gave approval for the study to proceed. The sponsor

Template No.: PCE_TP_CSC0016 Revision 2 Reference:

PCE_OP_CSC0014

Effective Date: 15Dec2019

and/or its representatives accessing the records and data will take all reasonable precautions in accordance with applicable laws, regulations, and guidelines to maintain the confidentiality of patients' identities.

Patients are assigned a unique identifying number; however, their year of birth may also be used in combination with this number to assist the sponsor to verify the accuracy of the data (e.g., to confirm that laboratory results have been assigned to the correct patient).

The results of studies – containing patients' unique identifying number, relevant medical records, and possibly year of birth – will be recorded. They may be transferred to, and used in, other countries which may not provide the same level of protection that applies within the countries where this study is conducted. The purposes of any such transfer and use may include: to support regulatory submissions, to conduct new data analyses to publish or present the study results, or to answer questions asked by regulatory or health authorities. The sponsor may transfer data collected in this study to its affiliates, collaborators, licensees and other companies and organizations working with or for the sponsor in connection with these purposes.

7.3.2. Potential Benefits

Potential benefits to patients with cancer include improved understanding of the benefits and risks of novel drug treatments for regulatory approval from the patient perspective and what patient, treatment and disease characteristics may influence treatment preferences for certain cancer types.

8. Intended Use of the Data

The data will be used to:

- Provide a better understanding of the experience of patients living with common and rare cancer types and what's important to patients, which ultimately could be used to design patient support interventions
- Identify and understand PP towards key endpoints used traditionally to assess efficacy and safety of oncology drugs, with implications for regulatory approval
- Provide a better understanding of the factors that influence cancer patient's treatment preferences about benefits and harms of cancer drugs

Template No.: PCE TP CSC0016 Revision 2 Reference:

PCE_OP_CSC0014

Effective Date: 15Dec2019

9. Documentation and reporting

A final study report will be generated after all data collection of the quantitative phase is complete. Following data collection and data analysis, a technical report detailing the objectives, methodology, results and interpretation/conclusions of the will be developed.

A plan for publication in a scientific journal will be determined with the Agency and will summarize the final study report. IQVIA will develop a scientific manuscript describing the methods and results of the PP study in people with cancer in Europe. IQVIA will prepare an outline of the paper and discuss this outline with the Agency. Based on the outline, IQVIA will construct one draft and one final version for review. After review, IQVIA will finalize the paper and submit the paper to a scientific journal (target journal to be agreed upon by the Agency and IQVIA).

10. Summary of Deliverables

Deliverables: PP study

- 1. Preliminary study plan/synopsis
- 2. a) Draft study protocol
 - b) Final study protocol

Registry of study in the EU PAS Register (http://www.encepp.eu/encepp/studiesDatabase.jsp)

- 3. Tools and material needed for the survey:
- Summary deck of literature review findings (PowerPoint)
- Conceptual model of treatment attributes (MS Word)
- Drafts (2) and a final Interview Guide (MS Word)
- Drafts (2) and final vignette and stated preference survey (MS Word)
- Drafts (2) and final Statistical Analysis Plan (MS Word)
